The primary outcome was Sever disease pain perception, which was determined by three ways: VAS, algometry and by the following question: "Do you have pain at sport activity?" which had

to be answered by YES or NOT (Sport Activity Pain dependent variable). The VAS is commonly used to measure pain perception (20), and has been used before to measure pain perception in children with calcaneal apophysitis (14,19). The VAS is described as a horizontal line 100 mm in length where at each end points the words “No pain” and “Worst imaginable pain” are placed (18,20). Participants were asked to mark the line at the point which best represents the level of pain intensity that they were experiencing (14). Algometry is commonly used to measure pressure-pain threshold (21). To perform the algometry, the Wagner FPX™ 25 Algometer (Wagner Instruments®, USA) was used. It had been used before in children with calcaneal apophysitis (10). To perform the algometry children were asked to lie down in prone position on the stretcher, with knee and ankle bent 90°. Then the algometer was positioned on the Achilles tendon insertion on the calcaneus. Three separate measurements were obtained and the average of them was taken as algometry value (10).

Secondary outcomes were to determine the values of the FPI and the Lunge Test in the children with Sever disease. The FPI was performed following the guidelines of Redmond et al (22). FPI is a 6-point tool for clinical assessment, which evaluates the multisegmental nature of foot posture in the three spatial dimensions. Each component of the test is graded between -2 and +2 (signs of supination or pronation), where neutral is graded with 0. Finally, a score range from -12 (highly supinated) to +12 (highly pronated) is obtained (22–24). Lunge Test is commonly used to determine shortness in triceps surae muscle (2,24). Restriction in the length of this muscle is considered when the dorsal flexion of the ankle is less than 38-35° (2,5,23,24).

Statistical analysis plan

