Sample size estimation was based on the detection of a difference of 29% in the number of children with pain; and a mean difference of 0.39 or superior for the algometry and the VAS, between baseline and after the follow up based on a previous pilot study (2). Assuming a two-side α of 0.05, power of 80%, and a 10% drop-out rate, a sample size of 198 participants was required. Continuous variables were expressed as mean \pm standard deviation (SD) whereas qualitative variables were expressed as frequencies and percentages. Continuous data were checked for normality by Kolmogorov-Smirnov Test.

The baseline characteristics of the children were summarized using descriptive statistics and tabulated for comparison between intervention groups. Baseline characteristics were compared between included and excluded participants to analyze whether they were representative. Mann-Whitney U and T-Student Tests were used to compare continuous variables and the Fisher Test to compare dichotomous variables.

Differences between baseline and final assessment were performed using the average-to-average method. Mann-Whitney U Test was used to compare absolute and relative changes in algometry and VAS. McNemar Test was applied to calculate the improvement, which was positive when subjects changed from pain situation to no pain situation for the dependent variable Sport Activity Pain. Identifying treatment effectiveness after the follow-up was made by regression models. Linear regression was applied to quantitative variables, algometry and VAS, and logistic regression to dichotomous qualitative variables, association was measured in terms of odds ratio.

Statistical analysis of the outcomes was performed according to intention-to-treat principles compared the groups regarding pain perception evolution. For all tests, a two-sided p-value <0.05 was considered significant. The statistical analyses were performed using the SPSS software 22.0 for Windows (SPSS Ibérica, Madrid, Spain).

REFERENCES

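### VAS and algometry are each tested on absolute change, on relative change and by an unspecified regression, with neither change score ranked; the tests can disagree, and which change score is stronger depends on inputs the plan does not give.

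*Combined protocol and SAP*

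**What the plan says.** The Outcome measures section makes VAS and algometry two of three expressions of one primary outcome: "The primary outcome was Sever disease pain perception, which was determined by three ways: VAS, algometry and by the following question". The third is a yes/no item on pain during sport.

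The Statistical analysis plan section then gives each of the two continuous measures three between-arm analyses:

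- Two rank tests: "Mann-Whitney U Test was used to compare absolute and relative changes in algometry and VAS".
- A regression: "Linear regression was applied to quantitative variables, algometry and VAS, and logistic regression to dichotomous qualitative variables".

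One sentence points towards an order: "Identifying treatment effectiveness after the follow-up was made by regression models". The threshold is the same throughout: "For all tests, a two-sided p-value <0.05 was considered significant".

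The section does not define relative change or say what to conclude if the two rank tests differ. It also does not say whether the regression outcome is the 12-week value, the absolute change or the relative change, or whether baseline is a covariate.

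**The concern.** Absolute and relative change answer different questions. Take relative change as change divided by the child's own baseline (an assumption, since the plan gives no definition). A child going from 10 to 0 mm on the VAS has improved by 10/10 = 100%, and a child going from 90 to 20 mm by 70/90 = 78%. On the relative scale the first child ranks higher; on the absolute scale (10 mm against 70 mm) the second does. Neither ranking is an error, but a trial that tests both needs to say which one answers its hypothesis. Relative change also has no value when baseline VAS is 0, and the eligibility criteria set no minimum pain score.

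The sentence on regression does not settle this. With its outcome unstated, the regression could itself be run on either change score. For each scale, then, one analysis can be significant and another not, with nothing fixed in advance to say which one counts.

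**Working it through.** **1. The plan's own figure.** The plan states "Assuming a two-side α of 0.05, power of 80%, and a 10% drop-out rate, a sample size of 198 participants was required", using "a mean difference of 0.39 or superior for the algometry and the VAS, between baseline and after the follow up" and a 29% difference in the proportion with pain. No SD, unit or base rate is given.

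For two means, n per arm = 2(1.96 + 0.842)²/d² = 15.70/d², rounded up, and the total is divided by 0.9 for drop-out.

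- 0.39 read as a standardised difference: 15.70/0.1521 = 103.2, so 104 per arm, 208 in total, and 208/0.9 = 232.
- 0.39 with an SD of 0.92: 88 per arm, 176/0.9 = 196.
- 0.39 with an SD of 0.93: 90 per arm, 180/0.9 = 200.
- The 29% difference: 54 to 118 in total, depending on base rate and continuity correction.

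So 198 is reached only with an SD of about 0.92–0.93, which the plan does not state. It can be neither confirmed nor called wrong.

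**2. Inputs for the simulations.** Evaluable children per arm: 198 × 0.9 / 2 = 89 (1:1 allocation assumed). Effect: 0.39/0.93 = 0.42 SD, back-solved from step 1 and not a figure in the documents. Baseline means, baseline coefficients of variation (CV), correlations (0.2–0.7) and the common change from baseline are all assumed.

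**3. Algometry, additive effect.** Baseline CV 0.25–0.5, correlation 0.5. Common gain is the improvement shared by both arms, as a share of mean baseline. Power is for the Mann-Whitney test.

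| Common gain | Absolute | Relative | Loss (points) | Tests disagree |
|---|---|---|---|---|
| 0% | 77–78% | 75–76% | 2–3 | 3–7% |
| 10% | 78–79% | 71–73% | 6–8 | 7–9% |
| 20% | 77–79% | 67–68% | 10–11 | 11–13% |
| 40% | 76–79% | 57–60% | 20 | 20–21% |
| 50% | 78–79% | 52–56% | 23–26 | 23–26% |
| 75% | 78–79% | 44–46% | 33–36 | 33–36% |

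A milder setting (baseline mean 6, SD 1.8; follow-up mean 7, SD 2; correlation 0.7) gave 95.9% against 90.8%, a loss of 5 points, with 5.8% disagreement.

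**4. Algometry, gain proportional to baseline.** The order reverses: relative change was stronger by 0.5 to 53 points. For example, with baseline CV 0.3, mean gain 50% and SD of gain 0.3, power was 65.9% absolute and 77.0% relative. Disagreement ranged from 4% to 57%.

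**5. VAS.** Baseline mean 65 mm, CV 0.2–0.4. Relative change ranged from 1 point weaker to 20 points stronger than absolute change. Disagreement was 3–26%, rising to about 42% when follow-up VAS lay near its floor.

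**6. The regression already in the plan**, taken as the 12-week value on arm and baseline (3,000 trials per scenario; correlation 0.2–0.7 in the additive model):

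| Setting | Absolute | Relative | Regression |
|---|---|---|---|
| Algometry, additive | 62–95% | 44–81% | 80–97% |
| VAS, additive | 56–92% | 77–91% | 80–96% |
| Algometry, proportional | 48–70% | 76–79% | 70–76% |
| VAS, proportional | 58–61% | 77–78% | 73–76% |

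The regression was never more than 7 points below the best of the three. Absolute change fell up to 28 points short of the best, and relative change up to 36.

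**7. No treatment effect.** At least one of the two change tests was significant in 4.5–8.6% of trials. Two independent tests would give 1 − 0.95² = 9.75%. Counting the regression as well, the figure was 8–9% per scale.

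**The case against.** The strongest reply is that the plan does contain an order: it says effectiveness is identified by regression, so the rank tests could be read as descriptive support. That is partly right, and it is why the fix builds on the regression. It does not close the gap, because the regression's outcome and covariates are missing and the rank tests carry the same significance threshold.

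A reader might infer three stronger things, none of which the documents support.

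- *Relative change is the weaker test for algometry, by a fixed margin.* The documents give no mean, SD, correlation or expected gain. The loss runs from almost nothing to over 30 points under an additive effect, and the sign reverses under proportional gain.
- *The two tests often disagree.* With no common change from baseline they do so in only 2–9% of trials. Higher rates need a sizeable shared improvement. That is plausible, since both arms receive a device plus advice on stretching, ice and activity, but it is not a stated figure.
- *Low baselines badly distort relative change.* The Design section stratifies VAS at 74 mm, which does not suggest many children with very low scores, and a rank test limits the influence of extreme percentages.

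It is also fair that the false-positive inflation from this pair is small, and that three unranked primary measures are the wider multiplicity problem.

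**Conclusion.** The concern holds as a gap in specification. Two of the three primary measures each have three between-arm analyses. Neither change score is ranked, relative change is not defined, and the regression that comes nearest to being the main analysis is not specified.

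Under the assumptions in the working, the absolute and relative tests disagree in about 6–26% of trials with a true effect when there is a moderate common change from baseline. The rate is lower without such a change, and higher when the change is large or follow-up VAS is near its floor. For algometry, relative change loses about 5–20 points of power when the effect is additive and the common gain is roughly 10–40% of baseline; it gains power when improvement is proportional to baseline. For VAS, relative change is usually the stronger. False positives from the pair reach about 5–9% per scale.

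All these sizes rest on assumed inputs. That the better change score cannot be known in advance is itself the reason to name one analysis now. The plan should make this change, but the point does not undermine the design.

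**What to change.** In the Statistical analysis plan section:

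1. State that the single between-arm test for VAS, and likewise for algometry, is the linear regression of the 12-week value on arm and baseline value.
2. Strike relative change from the Mann-Whitney sentence, and label the Mann-Whitney test of absolute change as supportive.
3. Define percentage change, including how a baseline VAS of 0 is handled, and report it by arm as median and quartiles without a p-value.

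The change should be made before outcomes are compared by arm. If that comparison has already been done, report all three analyses and say that the choice came afterwards.

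The cost is a few sentences and no new data, since baseline is already measured. Percentage change loses its p-value. If gain is truly proportional to baseline, the regression gives up about 3–7 points of power against relative change in the settings tabulated, and could give up more with a very wide baseline spread. The change does not settle which of the three pain measures is primary; that needs its own sentence.

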Following this line, there are some studies in literature that have used orthoses to act both on ACPS and the repetitive impacts (8,11,12,14–16). Orthoses provide support in the medial arch (relaxing plantar fascia), include a heel-lift component and a wider support surface (dispelling impacts) (8,11,12,14–16). The available evidence reported the use of orthoses (8,11,14), but most of them were prefabricated and the studies reveal statistical analysis and methodological

concerns that limit the validity of the results reported (9,16,17). Nor studies have previously compare the use of “off-the-shelf” with custom-made orthotics (16).

Objective

The present research wanted to provide a pragmatic randomized controlled trial with an intervention period of 12 weeks, with the aim to compare heel pain perception in children with calcaneal apophysitis using a custom-made Ethyl Vinyl Acetate foot orthoses and “off-the-shelf” heel lifts. Therefore, it was hypothesized that the primary outcome, pain relief, would be significantly improved with the custom-made orthosis compared to the heel lift.

Design

The study was a parallel-group, randomized controlled trial with concealed allocation, blinding of investigators and assessors and intention-to-treat analysis. It examined the effect of custom-made foot orthoses and heel lifts in children with calcaneal apophysitis. Participants were enrolled at the time of Sever disease diagnosis. After baseline assessment, children were individually randomized to “custom-made foot orthoses” (experimental group) or “off-the-self heel lifts” (control group). Concealed allocation was carried out by having randomization performed by a third party who was not involved in the recruitment and treatment of the children. Eight permuted blocks were used to stratify randomization by BMI (20 versus > 20 kg/m 2), Lunge Test (35 versus $> 35^\circ$ of dorsal flexion), FPI (4 versus > 4) and by VAS score (74 versus > 74 mm) because these were considered as important risk factors associated with pain severity in Sever disease (2,14,18,19). A researcher who was unaware of the randomized group allocation measured the outcomes at baseline and 12 weeks later. The design of the present research was based on and executed according to the CONSORT Statement. The study was approved by the Ethics Committee of Clinical Research of Aragón (C.P.-C.I.PI16/0303)

Participants

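### Improvement in sport-activity pain is tested with McNemar, which cannot compare the devices, and the plan does not say that the under-specified logistic model decides instead

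*Combined protocol and SAP*

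**What the plan says.** The Objective states a hypothesis between arms: "pain relief, would be significantly improved with the custom-made orthosis compared to the heel lift". Under Outcome measures, pain perception is measured by VAS, by algometry and by a question on pain at sport, "to be answered by YES or NOT (Sport Activity Pain dependent variable". It is the only yes/no outcome that the protocol defines.

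The Statistical analysis plan then has three relevant statements.

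- Absolute and relative changes in VAS and algometry are compared with the Mann-Whitney U test, a two-sample test.
- For Sport Activity Pain, "McNemar Test was applied to calculate the improvement, which was positive when subjects changed from pain situation to no pain situation".
- Next: "Identifying treatment effectiveness after the follow-up was made by regression models", with linear regression for VAS and algometry and "logistic regression to dichotomous qualitative variables, association was measured in terms of odds ratio".

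The closing paragraph adds: "Statistical analysis of the outcomes was performed according to intention-to-treat principles compared the groups regarding pain perception evolution". The section lists no model terms, and does not say which of McNemar and the logistic model settles the result for sport pain. The sample size refers to "detection of a difference of 29% in the number of children with pain" without a base rate, and without saying whether the 29% is absolute or relative.

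**The concern.** McNemar uses only the children whose answer changed, and asks whether more went from pain to no pain than the reverse. Run by arm or pooled, it contains no treatment contrast. For change in pain, the two continuous measures therefore get a two-sample test while the binary one gets a within-child test.

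Change over time is weak evidence about the devices here. Under Interventions, every child is given advice on stretching, ice and reducing sport intensity, so both arms may improve whichever device is worn. Under Participants, eligibility rests on age and radiological diagnosis, with no requirement for sport pain at baseline. A child who answers no at baseline cannot improve in the sense defined, so the baseline answer belongs in the analysis.

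At stake is which result is read as the answer. If a McNemar p-value is taken as evidence of effectiveness, it can look the same when the devices differ and when they do not. In some settings it can come out significant in one arm only, by chance.

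**Working it through.** **Inputs.** From the Statistical analysis plan: N = 198, 10% drop-out, two-sided 0.05. Assumed: 1:1 allocation (no ratio is stated), and all improvement and worsening rates (none is given). Evaluable children: 198 × 0.9 = 178.2, taken as 178, or 89 per arm. The 198 cannot itself be reproduced, because base rate, SD and allocation ratio are missing. It serves here only as the trial's size.

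**Step 1: equal true change in both arms.** Let p be the probability that exact McNemar is significant in one arm, found by enumerating all outcomes for 89 children. The arms are independent, so exactly one is significant with probability 2p(1 − p), which cannot exceed 0.50 (reached at p = 0.5). With 5% worsening in both arms:

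| Improving, both arms | p | Exactly one arm significant | Both significant |
|---|---|---|---|
| 5% | 0.020 | 4.0% | 0.04% |
| 10% | 0.154 | 26.0% | 2.4% |
| 15% | 0.488 | 50.0% | 23.9% |
| 20% | 0.787 | 33.6% | 61.9% |
| 25% | 0.937 | 11.8% | 87.8% |
| 30% | 0.987 | 2.6% | 97.4% |
| 34% | 0.997 | 0.6% | 99.4% |

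For example, at 15% improving: 2 × 0.488 × 0.512 = 0.50. The last row is a net fall of 34 − 5 = 29 points from baseline.

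**Step 2: large improvement.** 20,000 simulated trials, assuming that all children have pain at baseline and none worsens:

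| Pain resolved, orthosis vs heel lift | McNemar significant in both arms | Between-arm test significant |
|---|---|---|
| 50% vs 50% | 100% | 4.7% |
| 80% vs 51% | 100% | 98.8% |

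McNemar gives the same answer in both rows; the between-arm test separates them.

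**Step 3: one trial by hand.** With no worsening, the two-sided exact McNemar p-value is 2 × 0.5^k for k children resolved.

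- 45 of 89 resolved in each arm: McNemar p = 2 × 0.5^45 = 5.7 × 10⁻¹⁴ in both; Fisher between arms p = 1.0.
- 71 of 89 vs 45 of 89: McNemar p = 8.5 × 10⁻²² and 5.7 × 10⁻¹⁴; Fisher p = 0.00007. Odds ratio (71 × 44)/(18 × 45) = 3.86; risk difference 79.8% − 50.6% = 29.2 points.

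**Step 4: can the trial support a between-arm test?** Take an absolute 29-point difference centred on 50% (64.5% vs 35.5%, assumed). The standard error is √(2 × 0.25/89) = 0.0750 under the null and √(2 × 0.645 × 0.355/89) = 0.0717 under the alternative. Then z = (0.29 − 1.96 × 0.0750)/0.0717 = 1.99, so power is 97.7%. Across assumed higher-arm rates of 30% to 99%, power runs from 97.7% to 99.99%. No larger sample is needed.

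**The case against.** The strongest reply is that the plan already separates the roles: McNemar describes improvement, regression identifies effectiveness, and the intention-to-treat comparison is between groups. This largely stands. A reader might infer from the McNemar sentence that sport pain has no between-device analysis. The documents do not support that, because logistic regression is named for dichotomous variables and sport pain is the only such outcome. What remains is that its terms are not written out and it is not given precedence.

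A reader might also infer that two within-arm p-values will be contrasted, with a 50% risk of a false difference. The plan does not say this, nor even that McNemar is run by arm. The 50% is the most that 2p(1 − p) can be, and it arises only near particular assumed rates; it is 4% at 5% improving and 0.6% at 34%.

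Finally, it is tempting to say that an odds ratio contradicts the scale on which the trial was sized. The 29% is not stated to be absolute, and the sizing sentence words its differences as baseline against follow-up, so a between-arm risk-difference scale is an inference. An odds ratio is a valid effect measure. A risk difference would make the result easier to read, but leaving it out is not an error.

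**Conclusion.** The point holds in a limited form. McNemar cannot answer the trial's question for sport pain. The model that can is named, but without baseline or stratification terms and without a statement that it decides. That McNemar has no treatment contrast follows from the test and needs no assumption. The size of the possible confusion does rest on assumptions: 89 per arm, 1:1 allocation and the rates shown. Under equal true change with 5% worsening, exactly one arm is significant in 0.6% to 50% of trials over 5% to 34% improving; with large improvement both arms are significant whatever the device effect. The plan is not invalid on this point. This is an improvement to be had at almost no cost.

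**What to change.** In the Statistical analysis plan:

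1. Label McNemar and the before/after counts by arm as descriptive, and state that they are not evidence of a difference between devices.
2. Name one deciding analysis for Sport Activity Pain: logistic regression of pain at 12 weeks (yes/no) on arm, baseline sport pain and the stratification factors (BMI, Lunge Test, FPI, VAS), by intention to treat, with the arm term as the test of the hypothesis.
3. Report a risk difference with 95% CI beside the odds ratio, as a supplement.

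The cost is a few sentences of SAP wording and one regression. All variables are already collected, and neither the sample size nor the visits change.

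### Intention-to-treat is claimed, but every named analysis needs the single 12-week value and no way of including children without it is given, so by default the analysis is complete-case

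*Combined protocol and SAP*

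**What the plan says.** Intention-to-treat is stated twice. The Design section lists "blinding of investigators and assessors and intention-to-treat analysis", and the Statistical analysis plan says "Statistical analysis of the outcomes was performed according to intention-to-treat principles". Neither place defines the analysis set.

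The Design section gives one follow-up: the assessor "measured the outcomes at baseline and 12 weeks later". The Statistical analysis plan then names three kinds of outcome analysis:

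- For the continuous outcomes, "Mann-Whitney U Test was used to compare absolute and relative changes in algometry and VAS".
- For sport activity pain, a McNemar test of moves from pain to no pain.
- For treatment effectiveness after follow-up, linear regression (VAS, algometry) and logistic regression (the yes/no outcome), with no covariates named.

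Loss to follow-up appears only in the sample-size paragraph, as "a 10% drop-out rate" within the statement that "a sample size of 198 participants was required". The plan has no imputation, no named complete-case set and no sensitivity analysis for missing outcomes. It does plan to compare baseline characteristics of included and excluded participants, without saying who counts as excluded.

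**The concern.** A child who misses the 12-week visit has no post-baseline outcome. Without that value there is no absolute or relative change, no McNemar pair and no regression outcome. Unless values are filled in, which the plan does not mention, the child drops out of every comparison. The result is a complete-case analysis reported under an intention-to-treat label.

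What is at stake is bias. The Scientific Background describes the condition as benign and self-resolving, and the Interventions section asks for many hours of wear each day. A child might not return because the heel stopped hurting or because the device was unsatisfactory. The devices differ by arm, so the balance of these reasons may differ too. If it does, the children who return are no longer a fair comparison between the arms.

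**Working it through.** **Inputs from the documents.** N = 198; assumed drop-out 10%; "Assuming a two-side α of 0.05, power of 80"%; "detection of a difference of 29% in the number of children with pain"; visits at baseline and 12 weeks only.

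**Inputs assumed, because the documents do not give them.** Equal allocation (99 per arm); the 29% read as a between-arm difference among completers; completer proportions in pain of 64.5% (heel lifts) and 35.5% (orthoses), centred on 50%; missing fraction by arm.

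**Step 1: the plan's own figure.** The 198 cannot be reproduced, because no standard deviation and no pair of proportions is given. Reading 0.39 as a standardised difference gives n = 2(1.96 + 0.84)²/0.39², rounded up to 104 per arm. That is 208 in total, and 208/0.9 rounds up to 232. The 29% difference needs at most 46 per arm, and 92/0.9 rounds up to 103 (118 with a continuity correction). Neither gives 198. This is a separate matter; here 198 is taken as stated.

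**Step 2: children omitted by default.** 0.10 × 198 = 19.8, about 20, leaving about 178 (89 per arm). If 198 was built as 180 × 1.1, the allowance is 18.

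**Step 3: which analyses need the 12-week value.**

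| Analysis | Needs | Child with baseline only |
|---|---|---|
| Mann-Whitney on change | both values | omitted |
| McNemar | a before/after pair | omitted |
| Linear or logistic regression after follow-up | 12-week outcome | omitted |

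**Step 4: how far the sport-pain difference could move.** Let m be the fraction missing in each arm and x the proportion of missing children in pain (L = heel lifts, O = orthoses):

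D = [0.645(1 − m) + x_L·m] − [0.355(1 − m) + x_O·m]

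With m = 0.10:

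- All missing pain-free, or all in pain: 0.5805 − 0.3195 = 0.261 either way.
- Missing orthosis children all in pain, missing heel-lift children all pain-free: 0.5805 − 0.4195 = 0.161.
- The reverse: 0.6805 − 0.3195 = 0.361.

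The range is therefore 16.1 to 36.1 points. It depends on the 29-point difference and on m, not on the two proportions chosen. With m = 0.05 it is about 22.6 to 32.6; with m = 0.20 it is 3.2 to 43.2.

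With equal loss, filling in both arms the same way cannot show differential bias. With an unequal split of 5% (orthoses) and 15% (heel lifts), also assumed, all pain-free gives 0.548 − 0.337 = 0.211 and all in pain gives 0.698 − 0.387 = 0.311. The opposite extremes are again 0.161 and 0.361.

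**Step 5: is the extreme still significant?** At m = 0.10 the pooled proportion is (0.5805 + 0.4195)/2 = 0.50, and SE = √(2 × 0.25/99) = 0.0711. Then z = 0.161/0.0711 = 2.27, two-sided p about 0.02. Rounded to whole children (58 and 42 of 99), Fisher's test gives about 0.03. At m = 0.20, twice the planned allowance, z = 0.032/0.0711 = 0.45 and significance is lost.

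**VAS and algometry.** The documents give no standard deviation, and 0.39 has no unit, so no comparable range can be computed.

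**The case against.** The strongest reply is that the plan is silent rather than contradictory. It does not prescribe a complete-case analysis, and each named test could be run on imputed values. That stands: complete-case is the default consequence, not a written rule. But the intention-to-treat label promises that all randomised children are included, and no means of doing so is given.

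Other readings are tempting but not supported:

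- *Twenty children were lost.* The 10% is a planning allowance; the documents report no actual loss.
- *The analysis is unadjusted.* That is true of Mann-Whitney and McNemar. The regressions carry the effectiveness claim, and their covariates are simply not stated.
- *Nothing planned could reveal selective loss.* The comparison of included and excluded participants might cover drop-outs, although it may concern eligibility only. Even then it looks at baseline characteristics, is not stated by arm, and cannot show that loss depended on 12-week pain.
- *The trial is short of power because of drop-out.* The 198 already includes the allowance. Inflation protects precision, however, and does nothing against bias.

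The undefined average-to-average method might retain a drop-out's baseline value. If it compares group averages, it would set all children at baseline against completers at 12 weeks, and drop-outs would still have no 12-week outcome.

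**Conclusion.** The concern holds as a gap between the stated principle and the stated analyses. By default about 20 of 198 children would be omitted at the assumed 10%, with no check for loss related to 12-week pain.

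For sport pain, under the assumptions in the working, a 29-point completer difference corresponds to between 16 and 36 points in all randomised children. A reader might infer that missing data could overturn the sport-pain result. At 10% loss per arm that is not supported: the most adverse case keeps its direction and stays significant. The consequence is uncertainty about the size of the effect and an inaccurate label. If loss were well above 10%, that reassurance would not hold. For VAS and algometry the effect is unquantified. This should be corrected, but it does not by itself invalidate the trial.

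**What to change.** 1. Define the analysis set as all randomised children, analysed as allocated.
2. Make the between-arm estimate a regression of the 12-week outcome on arm (linear for VAS and algometry, logistic for sport pain), adjusted for the baseline value and the stratification factors in the Design section (BMI, Lunge Test, FPI, VAS).
3. Fill in missing 12-week values by multiple imputation within arm, from baseline VAS, algometry, sport pain, BMI, Lunge Test and FPI. With baseline data only, this adds little information beyond the adjustment in item 2; it keeps every randomised child in the analysis and provides the base for item 5.
4. Report the number lost and the reasons, by arm.
5. Add sensitivity analyses that depart from missing-at-random. For sport pain, count missing children as still in pain, then apply opposite extremes by arm. For VAS and algometry, worsen the imputed values in one arm stepwise until the conclusion changes.
6. If this is not done, call the analysis complete-case in the plan and the report.

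The cost is a little more analysis work on data the plan already collects, and possibly a slightly wider interval. Apart from recording why children did not return, no new measurement is needed.
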